6.4.3 Adjudication Panel

The adjudication panel will consist of at least three physicians. A minimum of three physicians will review each case.

6.4.4 Adjudication Process

The DCC will prepare a packet of materials to be express mailed to members of the panel. The packet will include: a summary of the patient's demographic information, diagnoses, and bleeding grade history. Before sending the materials, the DCC will remove any information that could identify the patient or disclose the treatment group assignment. The panel may request additional information including hospital records or autopsy reports. Panel members will complete Form P100 – Adjudication Form to indicate their conclusions. The P100 sheets will be sent to the DCC for entry into the data management system. If all panel members agree as to whether bleeding was a cause of death, no further action will be taken. If the panel members do not agree, a conference call will be scheduled to resolve the adjudication.

A summary of the panel's findings will be presented to the DSMB during their semiannual meetings.

6.4.5 Adjudication Schedule

The adjudication panel will review cases once every 6 months, approximately 1 month before each scheduled DSMB review of the Trial. Cases to be included in each review include deaths that occurred at least 30 days prior to the review, meet one or more of the criteria listed in Section 6.4.2 and have not yet been reviewed by the panel.

7. ADVERSE EVENT CRITERIA AND REPORTING

Reporting of all adverse events will be consistent with standard TMH CTN procedures described in the Manual of Procedures (MOP), Chapter 6: Guidelines for Reporting Adverse Events. Reporting requirements are calibrated to the severity of the event and the perceived relationship to the individual transfusion. The TMH CTN will be using the descriptive terminology developed by the National Cancer Institute (Common Terminology Criteria for Adverse Events (CTCAE) version 3.0 dated June 10, 2003) for use in reporting adverse events. The CTC includes a grading (severity) scale for each adverse event term. Grades were developed using the following guidelines:

Grade 0 - No adverse event or within normal limits

- Grade 1 Mild adverse event
- Grade 2 Moderate adverse event
- Grade 3 Severe adverse event
- Grade 4 Life threatening or disabling adverse event
- Grade 5 Fatal adverse event

7.1 Definitions

Adverse Event: Any unfavorable and unintended sign (including an abnormal laboratory finding), symptom or disease temporally associated with the use of a medical treatment or procedure regardless of whether or not it is considered related to the medical treatment or procedure (attribution of unrelated, unlikely, possible, probable, or definite).

Serious Adverse Event: Any adverse event that results in any of the following outcomes: Death, a life threatening event, prolongation of existing hospitalization, congenital anomaly/birth defect, and/or a persistent or significant disability/incapacity.

7.2 Data Collection and Validation

In general, data will be collected and entered into a web-based data management system (DMS) at each site participating in the Platelet Dose Trial, and transferred electronically to the Data Coordinating Center. The DMS is programmed to validate all data entry fields as the data is entered. Validations are question-by-question checks that give immediate

feedback to help catch data entry errors, form completion errors, or out-of-range values. Reports of outstanding edits, generated upon completion of data entry, will enable continuous cleaning of data at each site.

[figure not shown]
The DCC will regularly monitor all data for consistency and correctness. If the DCC observes inconsistent data or patterns of protocol violations or missing data, site staff will be contacted immediately to address the finding.

7.3 Monitoring of Adverse Events

Serious adverse events, including death, will be monitored continuously by the DCC as data are received. Transfusion related events of Grade 3 and higher will be monitored by the DCC at least monthly.

Whenever the continuous or monthly monitoring raises concern about event rates, the DCC will immediately contact NHLBI. Details are provided in subsections 7.3.1 and 7.3.2. The NHLBI TMH Executive Secretary will contact the DSMB Chair to discuss any concerns raised by the continuous and monthly monitoring of adverse events. After review of the concerns with the DSMB Chair, an interim DSMB conference will be scheduled if deemed necessary.

Figure 1 summarizes the monitoring plan for this study.

7.3.1 Continuous Monitoring of Serious Adverse Events

Serious adverse events, including death of a subject participating in the Platelet Dose Protocol, must be reported to the DCC within 24 hours by phone or email. The Serious Adverse Event Form (Form P085) must be sent to the DCC via fax within 48 hours. The Serious Adverse Event Form will be entered into the Data Management System by the DCC. A summary of the adverse event must be submitted to the DCC within 10 days of the event. This category of events includes, but is not limited to, transient ischemic attack, myocardial infarction, stroke, Graft-versus-Host disease, venocclusive disease of the liver, seizure, TRALI, and death. It also includes other life-threatening and fatal (Grade 4 and 5) adverse events related to transfusion of blood products. These include life-threatening and fatal events related to allergic reaction/hypersensitivity, sinus bradycardia, sinus tachycardia, hypertension, hypotension, dyspnea, hypoxia, wheezing, cough, hemolysis, fever, and infection.

The DCC Medical Monitor assigned to the study will review all serious adverse events as data arrive at the DCC. In particular, the Medical Monitor will review the attributions listed on Form P085 regarding the relationships between the adverse event and transfusion, underlying disease and bleeding (unrelated, unlikely, possible, probable or definite). If an adverse event is reported on Form P085 as probably or definitely related to transfusion or bleeding, if the Medical Monitor thinks such an attribution might be warranted, or if other questions arise, the Medical Monitor will confer with a second non-study physician with expertise in transfusion medicine. In addition, each month these physicians will review together the attributions for serious adverse events that were not considered probably or definitely related to transfusion or bleeding.

The DCC will report all serious adverse events to the NHLBI Project Officer as described in the TMH MOP. Serious adverse events that are considered probably or definitely related to transfusion or bleeding (either on Form P085 or according to the Medical Monitor) will be flagged for special attention. In these cases, the Executive Secretary will contact the DSMB Chair to ask for advice on how to proceed.

7.3.2 Monthly Monitoring of Transfusion Related Events

Adverse events of all severity levels that are related to transfusion of blood products (i.e. events related to allergic reaction/hypersensitivity, sinus bradycardia, sinus tachycardia, hypertension, hypotension, dyspnea, hypoxia, wheezing, cough, hemolysis, fever, infection, and rigors/chills) will be monitored by the DCC using data reported on the Transfusion Related Event form (Form P012). Serious transfusion related adverse events are also reported within 24 hours, and monitored as described in Section 7.3.1.

At least monthly, the DCC Protocol Statistician will calculate the percentage of patients in each treatment arm with at least one transfusion related event of Grade 3 or higher. The Protocol Statistician and Medical Monitors will meet to review and discuss the results of this analysis. Transfusion related events of Grade 3 or higher

are expected to be rare. In this patient population, at most 1 - 3% of patients would be expected to have at least one such event. If any arm has more than 5% of patients with a Grade 3 or higher transfusion related event, and this percentage differs significantly from the percentage in at least one of the other arms as described below, the DCC will notify NHLBI. The Executive Secretary will contact the DSMB Chair to ask for advice on how to proceed. This monitoring plan is designed to identify a possible excess of transfusion related events in one or more study arms. It is not intended to serve as a formal stopping rule for this study.

Table 3 shows the p-values that would trigger notification of NHLBI if the 5% criterion were also met. For the first 14 months, the boundary p-value is 0.0010. At later months, the boundary p-values are similar to the O'Brien-Fleming boundaries at those months for a trial with a nominal p-value of 0.017 for each comparison. These boundaries were chosen, using simulations, to strike a balance between two goals: minimizing the chance of flagging a comparison for special attention when there is truly no difference between treatment arms, and maximizing the chance of flagging a comparison for special attention before the planned end of the trial when there truly is a difference between treatment arms and the highest rate is above 5%.

Month	p-value
1	0.0010
2	0.0010
3	0.0010
4	0.0010
5	0.0010
6	0.0010
7	0.0010
8	0.0010
9	0.0010
10	0.0010
11	0.0010
12	0.0010
13	0.0010
14	0.0010
15	0.0016
16	0.0022
17	0.0031
18	0.0042
19	0.0053
20	0.0066
21	0.0083
22	0.0098
23	0.0116
24	0.0137

 Table 3: P-values for interim monitoring of Grade 3+ transfusion related events

When there is truly no difference between the treatment arms the percentage of times that a comparison is flagged for special attention should be low. This will help protect the study from a decision to stop early for an imbalance in transfusion related events that is actually due to chance differences. When there truly is a difference between the treatment arms, and the highest percentage is more than 5%, the percentage of times that at least one comparison is flagged for special attention should be high. This will help to ensure that a treatment arm with excessive Grade 3 or higher transfusion related events is identified for special attention.

Table 4 shows the operating characteristics of this monitoring plan for transfusion related events under several different scenarios, as determined by simulations with 10,000 replications per scenario. In the three scenarios where the true percentage of patients with Grade 3 or higher transfusion related events is the same in all three treatment groups, there is less than a 2.5% chance that NHLBI would be contacted. In all of the eight scenarios where there are treatment arm differences and the highest rate is above 5%, there is at least a 68% chance that NHLBI would be contacted, indicating reasonable power to detect excessive Grade 3 or higher transfusion related events. In six of the eight scenarios there is at least an 80% chance that NHLBI would be contacted.

Scenario	True percentage with Grade 3+ transfusion related events			Percent of replications with comparison flagged for attention			Median month for the comparison to be flagged, among replications where the comparison is flagged				
	Arm A	Arm B	Arm C	Any	A vs. B	A vs. C	B vs. C	Any	A vs. B	A vs. C	B vs. C
1	1%	1%	1%	0.00%	0.00%	0.00%	0.00%	n/a	n/a	n/a	n/a
2	2%	2%	2%	0.23%	0.15%	0.09%	0.04%	16	17	17	10
3	3%	3%	3%	2.04%	0.76%	0.71%	0.76%	19	19	19	19
4	1%	1%	6%	89.20%	0.00%	87.48%	87.64%	13	n/a	14	14
5	1%	3.5%	6%	89.23%	12.12%	87.96%	26.30%	14	16	14	20
6	2%	2%	6%	82.84%	0.04%	73.05%	73.11%	16	11	18	18
7	2%	4%	6%	75.64%	13.88%	72.66%	15.71%	18	19	18	20
8	2%	2%	7%	95.68%	0.03%	90.35%	90.48%	15	16	16	16
9	2%	4.5%	7%	91.54%	27.90%	90.09%	22.70%	16	19	16	20
10	3%	3%	7%	80.72%	0.71%	65.23%	65.85%	18	20	19	19
11	3%	5%	7%	68.90%	18.28%	65.34%	13.58%	18	20	18	20

7.4 Interim Analyses and Statistical Stopping Guidelines

Formal interim analyses of the primary endpoint and selected safety-related endpoints have been developed to monitor the study. These formal interim analyses are designed to assist the DSMB in overseeing the study. The DSMB may develop other criteria for determining when to intervene in the enrollment or treatment of patients in the study if deemed necessary.

The DSMB will make its recommendations based on the totality of evidence, taking into account the observed rates in each treatment arm of the primary bleeding endpoint, other safety-related secondary endpoints, and adverse events; the conduct of the study (accrual, compliance, etc.); and information from outside the study. Therefore, the interim analysis plan will provide guidelines rather than strict rules about whether the study (or one arm of the study) should be stopped before its planned conclusion.

The proposed plan is as follows.

7.4.1 Interim Analyses of Primary Endpoint

Sample size calculations have been based on the assumptions that

- There will be four equally spaced looks planned for the primary endpoint, i.e. interim looks after outcome data have been obtained for approximately 112, 225, and 337 patients per arm, and a final look at the end of the study;
- The primary endpoint will be analyzed at each look using separate pairwise comparisons between each pair of treatment arms still enrolling patients at that look; and,
- A Lan-DeMets alpha spending function similar to O'Brien-Fleming boundaries will be used for each pair of treatments, with a nominal p-value of .017 for each pair (i.e. using Bonferroni adjustment for the three pairwise comparisons).

This approach controls the Type I error for each pair of treatments to be no more than 0.017 even if a decision is made to discontinue one treatment arm partway through the study.

This approach means that an extremely large difference between two treatment arms in the percentage of patients with Grade 2 or higher bleeding would be needed to cross a stopping boundary at the first look. The boundary becomes less stringent at later looks. If the study continues to its planned number of patients, the treatment difference needed to declare statistical significance will be only slightly larger than the critical value that would be used if there were no interim looks. Table 5 shows the p-values that would be needed for each one-degree-of-freedom chi-square test at each look to declare that the boundary had been crossed. At an interim look, this would suggest that stopping the trial, or one arm of the trial, should be considered. If the study continues to the planned number of patients, crossing the boundary would be

considered necessary to declare a statistically significant difference between the two arms with an alpha level of 0.017.

Look	p-value
1 st interim look	< 0.0001
2 nd interim look	0.0004
3 rd interim look	0.0046
Final look	0.0155

Table 5: P-value boundaries using Lan-DeMets O'Brien-Fleming type boundaries

If the DSMB meetings do not take place at exactly the planned number of subjects, the EAST-3 software package can be used to adjust the critical p-value at each look to ensure that the overall significance level of 0.017 for each pairwise comparison of the primary endpoint is maintained.

7.4.2 Interim analyses of safety-related secondary endpoints

Several of the secondary endpoints listed in Section 2.2 are related to patient safety. These include secondary endpoints 13 (highest grade of bleeding while on study), 14 (if a validated published severity scale which we can calculate from study data becomes available), 15a (death due to bleeding), and 17 (all-cause mortality).

At each scheduled DSMB meeting data will be presented regarding the proportion of patients in each treatment arm with death due to bleeding and with death from any cause. P-values for chi-square tests (or, for rare outcomes, Fisher's exact tests) comparing each pair of treatment arms will be provided. Data will also be presented regarding the proportion of patients in each treatment arm who reach each grade of bleeding, and Cochran-Mantel-Haenszel tests of trend (or similar exact tests, for rare outcomes) will be presented for each pair of treatment groups. If an ordinal severity scale is available, a similar approach will be taken. If an essentially continuous severity scale is available, it will probably be highly skewed. The mean, standard deviation, and quartiles of the score will be presented for each group. If a log transform or other suitable transform can be found, the data will be transformed before using t-tests to compare each pair of treatment arms. Otherwise, Wilcoxon rank sum tests will be used to compare each pair of treatment groups. For each of these secondary outcomes, the p-value boundaries in Table 5 will be used when considering whether to stop the trial or one arm of the trial.

Early stopping guidelines based on endpoints related to blood component usage or transfusion events are not proposed, because these endpoints are related to the economics of health care rather than patient safety.

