7.5.3 Semi-Annual DSMB Reports

The DSMB will meet every 6 months, either in-person or via teleconference. Reports will include:

- Baseline characteristics overall and by treatment arm;
- Formal interim looks at:
 - Primary study endpoint,
 - Highest grade of bleeding,
 - Death due to bleeding,
 - All cause mortality,
 - Bleeding severity (if validated scale available);
- Serious adverse events overall and by treatment arm;
- Transfusion-related events of all severity levels overall and by treatment arm;
- Site status;
- Accrual overall and by site; and
- Study compliance issues.

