8. STATISTICAL CONSIDERATIONS

8.1 Analysis Plan

The primary analysis for the primary endpoint, the percentage of patients with at least one episode of Grade 2 or higher bleeding, will be three one-degree-of-freedom chi-square tests, each comparing a pair of treatment groups. These tests will be carried out at the .017 significance level to adjust for the multiple comparisons.

These analyses will be done on an intention-to-treat basis. That is, patients will be counted in the treatment arm to which they were randomly assigned, even if they actually received transfusions that were not according to their assigned dosing strategy. Any such "crossovers" between treatment arms will tend to make the observed percentages of patients with Grade 2 or higher bleeding more similar between treatment arms than they would have been if all patients had been treated according to their assigned dosing strategy. Thus, an intention-to-treat analysis is conservative.

The most important secondary endpoints, capturing key data on costs and safety, are the total number of platelets dispensed, the total number of transfusion events, the highest grade of bleeding, and the bleeding severity score (if such a score has been validated and published by the end of the Platelet Dose trial, and the necessary information to calculate the score was collected). These endpoints capture the main components of transfusion costs and seriousness of bleeding. Differences between each pair of treatment arms for these three or four pre-specified key secondary outcomes will be tested, each at the .017 significance level, also on an intention-to-treat basis. For other secondary outcomes, only descriptive data will be presented.

Platelet usage, number of transfusion events, and the severity score (if continuous) are expected to have highly skewed distributions, so for these endpoints a log transform (or other suitable transform) will be carried out before using a t-test to compare treatment arms. If no acceptable transform can be found, a Wilcoxon rank sum test will be used instead of the t-test.

In the analysis of highest grade of bleeding, some grades are expected to be quite rare. Proc StatXact will be used for each of the 2x4 tables to obtain precise Monte-Carlo estimates of the p-value for an exact Kruskall-Wallis test for treatment differences, where the bleeding grades are considered ordered. If the severity score is ordinal, similar analyses will be carried out for that outcome.

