8.2 Sample Size and Power

The primary endpoint for the study is the percentage of patients with at least one episode of bleeding at Grade 2 or higher, as determined by the Platelet Dose Trial Bleeding Scale.

Eighty-five percent power was desired to detect an absolute difference of 12.5% between any pair of dose strategies. The estimated percentage of patients who will experience Grade 2 or higher bleeding is 50%. Sample size for a chi-square test at the .017 level was calculated for a scenario with true percentages of 43.75% and 56.25%, assuming an interim monitoring plan with three interim looks and one final look. (See section 7.2.) Without taking into account loss to follow-up, 389 patients per arm (1167 patients in all) would be needed to achieve 85% power. This sample size would also provide 80% power to detect a treatment arm difference if the true percentages were 44.1% and 55.9% (an absolute difference of 11.8%) and 90% power to detect a treatment arm difference if the true percentages were 43.3% and 56.7% (an absolute difference of 13.4%). A sample size of 445 per arm would be needed for 90% power to detect a difference with true percentages of 43.75% and 56.25%.

Because the patients in this study will be hospitalized, loss to follow-up is expected to be no more than 10%. Conservatively allowing for 13.5% loss to follow-up, the target sample size is 450 patients per arm (1350 patients in all).

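### No interim boundary targets non-fatal Grade 3-4 bleeding itself, and the all-grades trend test is weak if such bleeding is uncommon and an excess comes mainly out of Grade 2

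*Protocol*

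**What the plan says.** Section 7.4.2 lists the safety endpoints that are formally monitored: highest grade of bleeding, a severity score if a validated one appears, death due to bleeding, and all-cause mortality. The two death endpoints get a chi-square or Fisher test for each pair of arms. For highest grade, the DSMB sees the proportion reaching each grade by arm, and "Cochran-Mantel-Haenszel tests of trend (or similar exact tests, for rare outcomes) will be presented for each pair of treatment groups". The scores are not stated. Section 2.2 (item 13) gives the categories as Grade 1 or less, 2, 3 and 4.

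All of these are judged by the primary endpoint's boundaries: "For each of these secondary outcomes, the p-value boundaries in Table 5 will be used when considering whether to stop the trial". The same sentence extends this to closing a single arm. Section 7.5.3 repeats "Highest grade of bleeding" among the formal looks and does not separate out Grade 3-4. The primary endpoint, monitored under section 7.4.1, is Grade 2 or higher, yes or no.

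Two statements describe the expected distribution. Section 8.2: "The estimated percentage of patients who will experience Grade 2 or higher bleeding is 50" per cent. Section 8.1: "In the analysis of highest grade of bleeding, some grades are expected to be quite rare". No expected Grade 3-4 rate is given.

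**The concern.** A mean-score trend test over four ordered grades responds to the average shift in grade, measured against the spread of all grades. With about half the patients in the lowest category and most of the rest in Grade 2, that spread comes mainly from the lowest-versus-Grade-2 split. If one dose arm turns Grade 2 bleeds into Grade 3 or 4 bleeds, the average moves little and the Grade 2+ test does not move at all.

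Under section 6.3, Grade 3-4 includes bleeding that needs additional red cells and bleeding seen on CNS imaging, so it matters to the safety of a dose comparison. The protocol does treat a comparable hazard directly. Section 7.3.2 gives Grade 3+ transfusion-related events a by-arm comparison, p-value thresholds and simulated operating characteristics. Non-fatal Grade 3-4 bleeding has no such comparison of its own.

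**Working it through.** **Inputs from the protocol.** Section 7.4.1: "interim looks after outcome data have been obtained for approximately 112, 225, and 337 patients per arm"; a level set "with a nominal p-value of .017 for each pair"; on the boundary type, "A Lan-DeMets alpha spending function similar to O'Brien-Fleming boundaries will be used for each pair of treatments". Table 5 p-values are <0.0001, 0.0004, 0.0046 and 0.0155. Section 8.2 gives 50% at Grade 2+ and 450 patients per arm.

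**Reproducing Table 5.** O'Brien-Fleming-type spending at two-sided 0.017, with information 0.25, 0.5, 0.75 and 1, gives <0.0001, 0.000396, 0.00462 and 0.0155. Table 5 is correct.

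**Assumptions (not in the protocol).** Grade 3-4 is 3% or 5% in one arm and tripled in the other. Three quarters of Grade 3-4 is Grade 3. Scores are 1-4 unless stated. The first cut-off is taken as 0.0001. The excess is either moved out of Grade 2 (Grade 2+ stays at 50%) or added on top of it.

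**Approximation at the third look.** With n = 337 per arm, Δ the difference in mean score and V the pooled variance of the score, Z = Δ/√(2V/n). The chance of crossing is about Φ(Z − 2.83), where 2.83 is the two-sided normal value for p = 0.0046. Earlier looks add little.

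*3% versus 9%, Grade 2+ unchanged:*
- Δ = 0.045×1 + 0.015×2 = 0.075.
- The pooled grades are 50%, 44%, 4.5% and 1.5%, so the mean is 1.575, the mean square is 2.905, and V = 2.905 − 1.575² = 0.424.
- V is made up of 0.25 from the Grade 2+ split, 0.099 from the steps above Grade 2, and 0.075 from twice their covariance. The largest part is noise from a split that carries no signal here.
- Z = 0.075/√(2×0.424/337) = 1.49, so the chance of crossing is Φ(−1.34), about 9%.

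*Same case, Grade 3-4 as a proportion:* pooled rate 6%, Z = 0.06/√(0.06×0.94×2/337) = 3.28, so the chance is Φ(0.45), about 67%.

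*3% versus 9%, all excess added to Grade 2+:*
- Δ = 0.045×2 + 0.015×3 = 0.135.
- The pooled grades are 47%, 47%, 4.5% and 1.5%, so V = 2.995 − 1.605² = 0.419.
- Z = 2.71, so the chance is Φ(−0.13), about 45%.

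**Simulation.** One pair, Table 5 cut-offs, crossed by the third interim look:

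| Grade 3-4 | Excess | Trend, scores 1-4 | Trend, rank scores | Fisher on Grade 3-4 |
|---|---|---|---|---|
| 3% v 9% | out of Grade 2 | 8% | 2% | 64% |
| 3% v 9% | all added | 45% | 27% | 64% |
| 5% v 15% | out of Grade 2 | 27% | 6% | 93% |
| 5% v 15% | all added | 90% | 79% | 93% |

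If half the excess is added, the trend test (scores 1-4) crosses in 23% at 3% v 9% and 63% at 5% v 15%. By the end of the study, 3% v 9% with Grade 2+ unchanged gives 25% for the trend test and 91% for Fisher.

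**Both comparisons with the affected arm.** A tripled arm is compared with two others. Varying Grade 4 from 20% to 50% of Grade 3-4, with Grade 2+ unchanged, the trend test (scores 1-4) crosses in at least one comparison by the third look in 13-19% (3% to 9%) and 37-49% (5% to 15%). A chi-square test on Grade 3-4 crosses in 83% and 98-99%. With the excess added, the trend figures are 60-66% and 96-97%.

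**No difference.** At 5% v 5%, the Fisher test crosses in 1.1% of trials over all four looks, within the 1.7% allowed per pair.

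**The case against.** A trend test on an ordered endpoint is conventional, it matches the ordered analysis planned in section 8.1, and exact versions are allowed for rare outcomes. Nothing in section 7.4.2 is misstated. Four further points carry weight.

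1. A reader might infer that the trend test is the only interim test of serious bleeding. It is not. Death due to bleeding has its own pairwise test against Table 5, and fatal bleeding is Grade 4 by definition. The gap concerns non-fatal Grade 3-4 bleeding.
2. A reader might infer that a tripling of Grade 3-4 would rarely be caught. The protocol does not support that as a general statement. It gives neither a Grade 3-4 rate nor the scores, and it does not say that an excess would leave Grade 2+ unchanged. The trial is in fact powered for a shift in Grade 2+. At a 10% baseline, a tripling crosses by the third look in 89-95% of trials (scores 1-4, both comparisons) even with Grade 2+ unchanged. When Grade 3-4 is common and the excess raises Grade 2+, the trend test does about as well as a Grade 3-4 test.
3. Other safeguards exist. Serious adverse events judged probably or definitely related to bleeding are flagged, and the DSMB Chair is asked for advice (section 7.3.1). The DSMB sees the grade proportions, weighs all the evidence and may set further criteria (section 7.4). None of these, however, is a by-arm Grade 3-4 comparison against a boundary.
4. The added test gives little early protection. With the exact spending boundary it crosses at the first look in at most 0.1% of trials for rates up to 5% v 15%. By the second look, counting both comparisons, it crosses in 9% (2% to 6%) and 25% (3% to 9%). The strict early boundary limits any test.

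These points narrow the concern and make it less urgent. They do not supply the missing comparison.

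**Conclusion.** The concern holds in a limited form. Unless a severity score appears, non-fatal Grade 3-4 bleeding meets an interim boundary only through a trend test over all grades. That test loses most of its power when Grade 3-4 is uncommon and the excess comes mainly out of Grade 2. For one pair by the third look it then crosses in about 8% of trials against 64% (3% v 9%), or 27% against 93% (5% v 15%). The gap shrinks to 45% against 64%, and 90% against 93%, if all the excess adds to Grade 2+. The size therefore rests on assumed Grade 3-4 rates, on the unstated scores (rank scores are weaker still), and on where the excess comes from. This is a worthwhile, low-cost improvement to advisory monitoring and not an error in the plan's figures.

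**What to change.** In section 7.4.2, keep the trend test and state its scores. Add, for each pair of arms, a chi-square or Fisher exact test of the proportion whose highest grade is 3 or 4, judged against Table 5 as an advisory guideline. List it among the formal looks in section 7.5.3.

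The cost is one more row per DSMB report, from grades the coordinating center already assigns. The downside is one more guideline that could be crossed by chance: about 1% per pair over the trial with Fisher, against the 1.7% allowed. The gain comes mainly at the third look, partly at the second, and hardly at all at the first.
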